- Mean CGM glucose across days 2-7
- Proportion of time across days 2-7 within the CGM glucose range of 70-180 mg/dl
- Quality of life among study participants, their caregivers, partners and/or family members
- Treatment satisfaction among study participants, their caregivers, partners and/or family members

Safety endpoints

- Frequency of adverse events
- Frequency of severe hypoglycemia
- Frequency of diabetic ketoacidosis

Other endpoints

[figure not shown]
- Proportion of time across days 2-7 within each of the following CGM glucose ranges:
 - < 50 mg/dl
 - < 60 mg/dl
 - < 70 mg/dl
 - 70-120 mg/dl > 180 mg/dl
 - > 250 mg/dl
- Number of episodes of symptomatic hypoglycemia (reported daily by subjects)
- Percentage of subjects with mean Dexcom CGMG < 154 mg/dl (estimated average glucose corresponding to an A1c of 7%)
- MARD for the Dexcom G5 with the Contour Next One glucose meter as the reference
- Total daily dose of insulin
- Mean daily basal insulin dose
- Mean daily bolus insulin dose
- Total daily dose of glucagon
- Number of user-initiated glucagon doses
- Number of meal announcements
- Glucose variability measured with coefficient of variation (CV) and with mean of daily difference (MODD)
- Mean nausea severity from VAS
- Number of unscheduled insulin and glucagon cartridge/infusion set changes
- Mean glucose target

III. Study Design

III.a Overall Design

The study follows a 2-treatment, 2-period crossover design, 2 and will consist of two 7-day study arms in random order: one bihormonal bionic pancreas arm using insulin lispro or insulin aspart and dasiglucagon, and one insulin-only bionic pancreas arm using insulin lispro or insulin aspart, as seen in Figure 1.

Figure 7. Study design

Questionnaires will be administered to participants and their partners (designated contacts) at the beginning of the study and the end of each arm to gather data on attitudes towards bionic pancreas BG control, confidence, device burden and treatment satisfaction. This information will be used to make the best choices about how the final version of the bionic pancreas should be configured and used.

III.b Scientific Rationale for Study Design

A crossover study design was chosen to reduce the impact of inter-subject variability and to increase the statistical power to detect differences in secondary outcomes despite the relatively small number of subjects.

III.c End of Study Definition

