The study will end for subjects when they have completed the second follow-up visit scheduled 25 (\pm 4) days after the final day 7 visit, or at the time they chose to withdraw from the study or are removed from the study by decision of the principle investigator.

VI. Subject Selection

VI.a. Inclusion Criteria

Subjects

1. Age \geq 18 years and have had clinical type 1 diabetes for at least one year
2. Diabetes managed using an insulin pump for \geq 3 months
3. Prescription medication regimen stable for $>$ 1 month (except for medications that will not affect the safety of the participant and are not expected to affect any outcome of the study, in the judgement of the principal investigator)
4. Willing to wear one Dexcom CGM sensor, and up to two steel cannula infusion sets (6 mm Contact Detach) and change infusion sets frequently (if the subject is known not to tolerate steel infusion sets then a plastic set may be used)
5. Have used a CGM for at least one cumulative month over the last 24 months
6. Willing to stay within a 250-mile radius of the designated base throughout the study. Air travel is not permitted.
7. Informed consent obtained before any trial-related activities
8. Have a designated contact (an adult \geq 18 years of age) willing to serve as an emergency contact for them throughout the study.

Designated Contacts

1. Age \geq 18 years
2. Have an established relationship with the study participant
3. Willing to answer questionnaires about their experience with the participant's diabetes and the bionic pancreas
4. Willing to answer calls and check on the participant's wellbeing as needed
5. Able to provide informed consent (e.g. no condition that impairs cognition or judgement)

VI.b. Exclusion Criteria

1. Unable to provide informed consent (e.g. impaired cognition or judgment)
2. Unable to safely comply with study procedures and reporting requirements (e.g. impairment of vision or dexterity that prevents safe operation of the iLet, impaired memory, unable to speak and read English)
3. Current participation in another clinical trial with administration of investigational drug.
4. Current participation in another diabetes-related clinical trial that, in the judgment of the principal investigator, will compromise the results of this study or the safety of the participant
5. Previous exposure to dasiglucagon (otherwise known as ZP4207)

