The iLet bionic pancreas system can administer bolus doses of each drug up to every five minutes. A single autonomous bolus of insulin will not exceed 3 units per 5-minute dose [30 µl] (except when it is in response to an isolated BG entry, where the dose will not exceed 12 units [120 µl]) and a single meal-priming dose, which is triggered by the user but automatically determined by the control system, will not exceed 18 units [180 µl]. A single bolus of glucagon will not exceed 80 µg [20 µl]. The iLet can administer as little as 0.10 µl (0.01 units of U-100 insulin) in single bolus doses. Insulin exposure is expected to be comparable to that of participants when not participating in the study. It is expected that the total daily dose of glucagon will be < 1.0 mg daily as in previous studies. The recommended dose of glucagon for adult patients suffering from severe hypoglycemia is 1 mg as a single injection. Mean glucagon levels in our previous inpatient studies have been above the normal fasting range for glucagon only 1% of the time. The mean daily glucagon dose in a previous 7-day outpatient study using the bihormonal BP at a set point of 100 mg/dl was 0.58 mg/day (range 0.20-0.90 mg/day). Our previous data using the bihormonal BP at a set point of 110 mg/dl, which will be used in this study, resulted in a mean daily glucagon dose of 0.41 mg/day (range 0.15-0.78 mg/day). The total dasiglucagon dose delivered over the 8-hour period of our in-clinic study was 0.59 mg (range 0.28-1.33 mg) compared with 0.73 mg (range 0.35-1.33 mg) Lilly Glucagon. Therefore, the glucagon exposure of subjects is expected to be modest.

Subjects will also be provided with an emergency **glucagon** kit, for treatment of severe hypoglycemia as needed.

VI. c. Devices

Infusion Sets: Participants will be provided with leur lock compatible infusion sets for both study arms. Participants will be instructed to replace both their glucagon infusion and their insulin infusion set every

other day throughout the study. If the infusion set fails for any reason during the experiment it will be replaced promptly..

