 - Study staff will verify the participants are aware of the hypoglycemia and taking action to treat it. Participants will be reminded of the protocol for hypoglycemia, and the study provider will ensure they understand and will follow study procedures. Participants will be encouraged to follow up with any questions or concerns. All contact with the participants in response to hypoglycemia alarms will be documented.
 - In the case of a low threshold alarm with no response from the participant and no success in locating them or their designated contact, the site principal investigator will be immediately informed. If remote monitoring shows ongoing hypoglycemia, a decision may be made to dispatch emergency medical services to the locations the participant is known to frequent.
 - Remote monitoring for hypoglycemia will be the same in both study periods.
- The remote monitoring system will generate an alarm if the CGM glucose is > 300 mg/dl for 90 minutes.
 - Participants will be reminded of the protocol for prolonged hyperglycemia, and the study provider will ensure they understand and will follow study procedures. Participants will be encouraged to follow up with any questions or concerns. All contact with the participants in response to hyperglycemia alarms will be documented.

- Remote monitoring for hyperglycemia will be the same in both study periods.

VI. d. iv. Visit Procedures

Day 1 Visit:

Participants may be trained on the operation of the all study devices in a group setting or may be trained one-on-one. Both the participant and the study staff must be satisfied that the participant is comfortable with the operation of all study devices before he/she begins the study. Additional training sessions may be arranged as needed.

- Participants will complete their baseline psychosocial questionnaires
- Their body weight, heart rate and blood pressure will be documented
- Blood will be drawn for a chemistry panel and complete blood count, and a baseline assessment of anti-drug antibodies.
- Study staff will review any changes in the participant's medical history or medications to ensure continued eligibility, and any adverse events that may have occurred since their screening visit. Study staff will specifically ask subjects if they had any infusion site reactions or other skin irritation in the past 7 days, and will document any reactions.

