- Participants will be trained on the insertion and use of the Dexcom G5 CGM. Participants will insert their own CGM sensor and study staff will confirm they are doing it correctly.
- Study staff will review all study procedures and policies (including the use of the Dexcom G5, the Contour Next One, the Precision Xtra ketone meter, and the iLet device) and the upcoming visit schedule.
- The Dexcom G5 will be calibrated by the participant using the Ascensia Contour Next One SMBG glucometer, and study staff will confirm they are doing it properly.
- Participants will be trained on the use of the iLet.
- The control algorithm will be initialized with the participant's current weight
- The participant will remove his/her own insulin infusion pump and the participant will set up and start the iLet under the supervision of study staff. Participants will be instructed to not take any further insulin outside of the iLet throughout the study.
- The staff will confirm that the iLet is functioning properly prior to discharging the participant.
- All participants will be given Dexcom G5 CGM sensors, an Ascensia Contour Next One SMBG meter with test strips, ketone meter with strips, insulin, dasiglucagon for the bihormonal study arm, a glucagon emergency kit, an iLet, iLet pigtail adapters and Contact Detach infusion sets (an alternate infusion set may be supplied if the subject is known not to do well with the Contact Detach).

Day 7/Day 1 Visit:

- There may be no washout between the two study arms or the washout period may be up to 7 days.
- At the end of the first 7-day arm, subjects will return to the clinic and answer the post questionnaires for the study arm.
- The body weight, heart rate and blood pressure of the subject will be documented
- Blood will be drawn for a chemistry panel and complete blood count.
- Study staff will review any changes in the participant's medical history or medications to ensure continued eligibility, and any adverse events that may have occurred since their last study visit. Study staff will specifically ask subjects if they had any infusion site reactions or other skin irritation in the past 7 days, and will document any reactions.
- The iLet and the study glucometer will be downloaded. The memory of the iLet will be wiped and

it will be re-initialized for the next study period.

- Participants will replace their CGM sensor and calibrate when prompted if they haven't already.

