The primary endpoint evaluates if the iLet system performs as designed, receiving CGM signals and delivering drug doses (insulin and, when applicable, glucagon) calculated by the control algorithm with an acceptable degree of reliability and accuracy. No formal test of the primary endpoint is planned.

The null hypothesis tested for the key secondary endpoint is:

The amount of hypoglycemia using the bihormonal configuration of the iLet is equal to the amount of hypoglycemia using the insulin-only configuration of the iLet.

The proportion of time with CGM glucose < 54 mg/dl across days 2-7 estimates the amount of hypoglycemia.

VII.b Sample Size Determination

No formal statistical comparisons have been done for this study. This study is primarily intended to verify that the iLet is operating as expected (based on its design and on bench testing) in each configuration in the outpatient setting. A sample size of 10 subjects in a crossover design is considered adequate for this purpose.

VII.c Populations for Analyses

Adult subjects (≥ 18 years old) with type 1 diabetes.

VII.d Statistical Analyses

VII.d.i General Approach

An intention-to-treat analysis will be performed. Descriptive statistics will be used to summarize patient characteristics and assessments. No formal testing will be conducted to establish superiority. In general, all data will be summarized with descriptive statistics for each treatment group. Unless otherwise specified, continuous data will be summarized by presenting the number of non-missing observations, mean, standard deviation (SD), median, minimum, and maximum. Categorical data will be summarized by presenting the number of patients and percentage for each category. P-values can be displayed to aid interpretation, not for inference. Tables, figures and listings of all primary, secondary and safety endpoints will be created.

Baseline and demographic data will be summarized using descriptive statistics. All comparisons will be between treatments within patients. Listings of individual patient data will be presented.

Data from periods when the bionic pancreas was not in use will be included, if available (Dexcom CGM data may not be available in some failure modes). In cases where an arm was not completed we will use the available data from that arm in the data analysis.

VII.d.ii Analysis of the Primary Efficacy Endpoint

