- CGMG (CGM glucose) every five minutes from the Dexcom CGM
- All fingerstick BG measurements taken by the subject (meter download)
- Average glucose target used
- Insulin total daily dose from bionic pancreas download
- Glucagon total daily dose from bionic pancreas download
- Timing of meal announcements and size of meals announced from bionic pancreas download
- Time subjects were not under bionic pancreas control
- List of technical faults associated with the bionic pancreas including cause and resolution
- Body weight after each study arm
- Blood pressure after each arm
- Heart rate after each arm
- Skin reactions, if any, after each arm
- EKG after completion of the second arm, and at the first follow up visit if applicable
- Information collected from the daily email survey:

- Number of reported hypoglycemic events requiring carbohydrate intervention
- Total grams of carbohydrates taken to treat hypoglycemia
- Number of severe hypoglycemic events (defined as subject required assistance to treat)
- Mean nausea severity from VAS
- Number of unscheduled insulin cartridge/infusion set changes
- Number of unscheduled glucagon cartridge/infusion set changes
- Alcohol use (mean drinks per day)
- Exercise duration and exposure (duration X intensity)
- Data from questionnaires about attitudes and expectations regarding the bionic pancreas at baseline and on day 7 of each arm.

VIII. Risks and Discomforts

Subjects may experience mild discomfort associated with the insertion of infusion sets and the Dexcom CGM sensor into the SC tissues. The risk of discomfort due to insertion of infusion sets and sensors may be greater than in their lives outside the trial because more infusion sets and sensors are required than are used in usual care.

There is a risk of hypoglycemia. This risk is expected to be less than the risk during the subjects' lives outside of the trial based on data from earlier trials. All of our previous studies have shown that hypoglycemia is significantly reduced in all configurations of the bionic pancreas when compared with usual care.

There is a risk of hyperglycemia. This risk is expected to be less than the risk during the subjects' lives outside of the trial based on data from earlier trials. All of our previous studies have shown that hyperglycemia is significantly reduced in all configurations of the bionic pancreas when compared with usual care.

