There is a risk of headache, nausea or vomiting due to the administration of exogenous glucagon. There is a possible risk of skin rash due to administration of exogenous glucagon. There may be risks of daily, low-level glucagon administration that have not become apparent during trials lasting up to 11 days. Possible risks include changes in body weight, blood pressure or blood chemistries or blood counts, or development of anti-drug antibodies. The magnitude of the other possible risks due to daily administration of small amounts of glucagon are unknown, but are not expected to be high because mean glucagon levels have been in the fasted range in previous trials. Of note, the risk of nausea and vomiting has been low in prior studies. There may be other unknown risks associated with dasiglucagon.

IX. Potential Benefits

It is expected that this protocol will yield increased knowledge about using an automated closed-loop to control the glucose level. This research is one step on the path towards development of a fully closed-loop system, and is particularly important for establishing the safety and efficacy of a bihormonal system for larger and longer future studies. The individual participant may not benefit from study participation.

Based on evidence from previous trials of the bionic pancreas and the design of this trial, subjects enrolled in the study may benefit from a reduction in risk of hypoglycemia and hyperglycemia and a better mean glucose than they typically achieve.

Subjects will be financially compensated for participating in the study.

X. Data and Safety Monitoring

X. a. Monitoring of Source Data

During the experiment, CGM data, insulin dosing data, and glucagon dosing data will be automatically stored in the bionic pancreas device (from which it will be downloaded at intervals). All of the data will be combined in a single database that will be compared against the primary data files for integrity. The computer database will be backed up at least monthly and the backup media stored in a secure location.

Study staff will be encouraged to raise any concerns they may have or problems they have identified at any time. The PI, in consultation with the co-investigators, will decide a course of corrective action, and resolution or progress will be assessed no later than the next meeting.

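### Skin reactions are summarised by arm with no stated site or drug channel, so a local dasiglucagon effect cannot be separated from the effect of the second infusion set

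*Combined protocol and SAP*

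**What the plan says.** Section VII.e.ii lists the item as "Skin reactions, if any, after each arm". Under Visit Procedures (VI.d.iv), the question at the Day 1 and Day 7 visits is: "Study staff will specifically ask subjects if they had any infusion site reactions or other skin irritation in the past 7 days". Staff then document any reactions. The follow-up visits ask the same about the time since the last visit. Infusion-site reactions and other skin irritation share one question, and neither section says that the reacting site is noted.

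On analysis, the General Approach (VII.d.i) says that "all data will be summarized with descriptive statistics for each treatment group". Safety Analyses (VII.d.iv) presents adverse events by system organ class and preferred term for each group, without tests. Section X.c judges relatedness against the study intervention as a whole.

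On exposure, the trial "will consist of two 7-day study arms in random order". Subjects must accept "up to two steel cannula infusion sets", and the glucagon channel runs in one arm only, since supplies include "dasiglucagon for the bihormonal study arm". Under Devices (VI.c), "Participants will be instructed to replace both their glucagon infusion and their insulin infusion set every" other day; section VI.d.iii makes that a minimum frequency for each channel.

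Section VIII adds: "There is a possible risk of skin rash due to administration of exogenous glucagon". Unscheduled cartridge or set changes, by contrast, are listed separately for insulin and glucagon in VII.e.ii.

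**The concern.** The number of infusion sets is tied to treatment. Each subject has one set in place at a time in the insulin-only arm and two in the bihormonal arm, so the crossover balances subject characteristics but not the number of cannulas and adhesive patches. A count by arm adds any local effect of dasiglucagon to the mechanical effect of the second set.

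The confusion runs both ways. An excess produced only by the extra cannulas could be read as local intolerance of dasiglucagon, and a real local effect could be put down to the extra cannulas. Safety of both configurations is part of the study objective (section II), the DSMB reviews compiled safety data (X.b), and section IX presents the study as groundwork for larger and longer trials. Local tolerability of a new drug in a pump is something those trials would want to take from this one.

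**Working it through.** The documents give no reaction rate and no calculation on this point, so there is no figure to reproduce.

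**Inputs.** Arm length is 7 days (III.a). Sets are changed at least every other day in each channel (VI.c, VI.d.iii). There is one channel in the insulin-only arm and two in the bihormonal arm. One sensor is worn in both arms (VI.c). Ten completers are expected (V.a). The risk per set, p, is an assumption: 1% to 20%, equal in both channels, which is the case of no local drug effect.

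**Sets per subject and arm.** Placement on days 1, 3, 5 and 7 gives 4 sets per channel (7/2 = 3.5 on average). That is 4 against 8 per subject, and 40 against 80 over 10 subjects.

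**Expected count.** The ratio is 80p / 40p = 2.0 at any p. At p = 5% that is 2 against 4 reactions. If one sensor site per arm carries the same risk, the sites number 50 and 90, and the ratio is 90/50 = 1.8.

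**Subjects with at least one reaction, and chance of the observed ordering.** The first is 1 − (1 − p)^4 against 1 − (1 − p)^8. The second compares two independent binomial totals, on 40 and 80 sets.

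| p per set | Insulin-only, ≥1 | Bihormonal, ≥1 | Ratio | Bihormonal total higher | Tie | Lower |
|---|---|---|---|---|---|---|
| 1% | 3.9% | 7.7% | 1.96 | 42% | 41% | 17% |
| 2% | 7.8% | 14.9% | 1.92 | 56% | 25% | 19% |
| 5% | 18.5% | 33.7% | 1.81 | 73% | 12% | 14% |
| 10% | 34.4% | 57.0% | 1.66 | 86% | 6% | 8% |
| 20% | 59.0% | 83.2% | 1.41 | 96% | 2% | 2% |

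**Clustering within subject.** If subjects differ in reactivity (beta-binomial, assumed intraclass correlation 0.3, same propensity in both arms), the expected counts stay at 2:1. By simulation the bihormonal total is higher in 42%, 69% and 85% of trials at p = 2%, 5% and 10%.

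**What each summary shows when there is a local effect.** Let r be the risk at a glucagon site relative to an insulin site.

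- Arm count ratio: (4 + 4r)/4 = 1 + r. The no-effect value is 2, and r = 2 gives 3.
- Arm count ratio with one sensor site included: (5 + 4r)/5. An observed ratio of 2 then means r = 1.25, where infusion sites alone would mean r = 1. Without the site, the two cannot be told apart.
- Rate per set pooled over channels: (1 + r)/2. This is 1.0 with no effect, but r = 2 shows as 1.5 and r = 3 as 2.0.
- Rate per set by channel: r itself, with 1.0 under no effect.

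**The case against.** The strongest reply is that the trial compares two configurations and the second set belongs to one of them. Total skin burden by configuration is then a legitimate descriptive result, and section VIII already warns that more sets may mean more discomfort. That stands, and it is why the arm-level summary should stay.

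Second, the list in VII.e.ii is not the case report form, which is not in the documents. A reader might infer that the site is never captured. The documents do not support that; they show only that the protocol neither asks for it nor analyses it.

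Third, individual listings are planned and investigators review each event. At 5% per set about 6 infusion-site reactions are expected in all, few enough to read one by one. A reader might infer that a local effect could never be recognised, which goes too far. But a listing shows only what was collected, and relatedness to the whole intervention does not separate drug from cannula.

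Fourth, the rash named in section VIII is not said to be at the infusion site. A generalised rash need not scale with the number of cannulas and is a separate matter.

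Finally, safety is descriptive and the primary endpoint is device operation. This limits the weight of the point, but an untested comparison still carries the 2:1 exposure.

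**Conclusion.** The point holds as a limit on interpretation. As written, the plan cannot separate a local dasiglucagon effect from the effect of the second set. With no such effect, the expected infusion-site count is about 2:1, less when sensor sites are included or subjects are counted instead of events.

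These sizes rest on equal risk per set in both channels, adherence to the change schedule, and assumed rates; the table's probabilities also assume independent reactions. A reader might infer that the bihormonal arm is bound to show more reactions. It is not: at 1% to 2% per set, a tie or a reversal occurs in 44% to 58% of trials with 10 subjects. The primary endpoint and the glycaemic endpoints are unaffected. The change is worth making before enrolment, because the site is hard to recover later.

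**What to change.** 1. Add a site field to the existing skin-reaction question: insulin site, glucagon site, CGM site, or other/generalised.
2. Count the sets actually inserted per channel. Adding scheduled to unscheduled changes is not a true count: it assumes adherence to a minimum frequency, and the unscheduled item combines cartridge and set changes.
3. In VII.d.iv, keep the arm-level summary and add a descriptive table of reactions per set by channel. Compare glucagon with insulin sites within subject in the bihormonal arm, and insulin sites across arms. With equal risk per set and no local drug effect, both expected ratios are 1.0. Do not pool the rate over channels, since that dilutes a real effect. Report generalised reactions separately.

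The cost is one field, one count and one table, with no extra visit and no change to treatment. Recall of the site over up to 7 days will be imperfect. With about 40 glucagon sets the rates will be imprecise, so the table should be read as description. An insulin site is also not a drug-free control, so the within-arm comparison sets one drug's site against another's.
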